1.3.2. Multiple Ascending Dose (MAD) Cohorts 4-8

Procedure	Screening (Up to 28 days before Day 1)	Study Period (Days)									Follow-up (7-14 days post last dose) ¹ / Early Withdrawal ²	Notes
		-1	1	2	3	4	5	6	7	8		
Outpatient Visit	X										X	
COVID 19 Testing	X	←=====X=====→										Screening: frequency in accordance with site procedures. Day -1 to 8: Ad hoc testing based on clinical presentations and site procedures. Day 8: Sample collected upon discharge
Admission to Clinical Unit		X										
Inpatient Stay at Clinical Unit		←=====X=====→										
Discharge from Clinical Unit										X		Following completion of all assessments.
Informed Consent	X											
Inclusion and Exclusion Criteria	X											
Demography	X											
Full Physical Examination	X*					X					X	*The full examination will also include height measurement, weight and BMI Calculation. Refer to Section 8.1.1 for details of physical examinations.
Brief Physical Examination		X [§]		X						X		[§] BMI calculation at Screening and Day -1 will be verified against eligibility criteria. Additional exams/screens may be performed, or brief exams made full exams, by the Investigator, as deemed necessary (e.g. where safety or laboratory findings indicate). Tests will be conducted within site specified standards. Refer to Section 8.1.1 for details of physical

CONFIDENTIAL

208441
Protocol Amd 6

Procedure	Screening (Up to 28 days before Day 1)	Study Period (Days)										Follow-up (7-14 days post last dose) ¹ / Early Withdrawal ²	Notes
		-1	1	2	3	4	5	6	7	8			
													examinations.
Drug/Alcohol/Smoking Screen	X	X											Tests include alcohol breath test, smoking breath test and urine drug screen.
Medical/Medication/Drug/Alcohol History	X	X											
HIV, Hepatitis B and C Screening	X												
Holter Monitoring (24 hour)	X												
Haem/Chem Test	X*	X*	X	X*	X*	X	X*	X	X*			X*	Blood samples will be collected in a fasted state. * Include liver chemistry
Urinalysis Test	X	X	X	X	X	X	X	X	X			X	Urine Sampling: 
 - First void, where possible. - If trace protein in urine is detected, a repeat test can be performed (within 24 hours, except if the repeat test is required at Screening the site should repeat as soon as possible within the screening period). If results are considered abnormal (guidance in SRM), further quantification is required at the investigator's discretion. - CCI [REDACTED]

CCI [REDACTED]

CONFIDENTIAL

208441
Protocol Amd 6

Procedure	Screening (Up to 28 days before Day 1)	Study Period (Days)										Follow-up (7-14 days post last dose) ¹ / Early Withdrawal ²	Notes
		-1	1	2	3	4	5	6	7	8			
CCI													
Lactate Sampling			X	X			X					Blood sample to assess lactate at the following timepoints: 
- Day 1, 2 and 5: predose and post morning dose at 2hr, 4hr, 8hr, 12hr*, 16hr.- * (prior to evening dose) Assessment timepoints may be modified, as deemed necessary by the Investigator and sponsor.	
Telemetry			←X→					←X→				Continuous at least 48 hr post-morning dose on Day 1 and at least 24 hr post morning dose on Day 6. Initiate at least 15 min. prior to first dose on Day 1 and Day 6 respectively. If a waveform abnormality is detected, then extend for further 24hr	
Randomisation			X										
Study Treatment			X	X	X	X	X	X	X*			BID dosing: GSK3494245 or placebo will be administered using a 12hr dosing interval (morning and evening dosing). TID dosing: GSK3494245 or placebo will be administered using a 6 hr dosing interval (morning, afternoon and evening dosing) *Only single dose on last day of dosing period.	
12-Lead ECG	T	X	T	X	X	X	X	X	X		X	12-Lead ECG to be conducted on Day-1 and pre-dose Day 1 and then at the subsequent time points post first-dose: 30 min, 1 hr, 1.5hr, 2hr, 2.5hr, 4hr, 6hr, 8hr 12hr and 14hr. Day 2 to 7: 12-Lead ECG at pre-morning dose Timings will be reviewed as cohorts progress and may be adjusted to ensure appropriate measurements relative to peak concentrations for	

CONFIDENTIAL

208441
Protocol Amd 6

Procedure	Screening (Up to 28 days before Day 1)	Study Period (Days)									Follow-up (7-14 days post last dose) ¹ / Early Withdrawal ²	Notes
		-1	1	2	3	4	5	6	7	8		
												subsequent cohorts T = assessments done in triplicate, at Pre-dose only . If any abnormal ECG reading is recorded, refer to Section 7.1.5 for appropriate action.
Vital signs	X	X	T*	X	X	X	X	X	X	X	X	
Vital signs to include HR, BP, temperature and respiration rate. BP and HR will be assessed in a supine position.
 
Vital Signs to be conducted on Day-1 and pre-morning dose Day 1 and then at the subsequent time points post first-dose: 2hr, 4hr, 6hr, 8hr, 12hr and 14hr. Days 2-6: pre-morning dose assessments only. Vitals Signs to be conducted on pre-morning dose Day 7 and then at the subsequent time points post-morning dose; 2hr, 4hr, 6hr, 24hr (Day 8)
 
Timings will be reviewed as cohorts progress and may be adjusted to ensure appropriate measurements relative to peak concentrations for subsequent cohorts T = assessments done in triplicate, *At Pre-dose only (except tympanic temperature and respiration rate)

PK Blood Sampling			<=====X=====>									
PK samples will be collected at the following time points in case of BID administration: Day 1: pre-morning dose, 10min, 30min, 1hr, 1.5hr, 2hr, 2.5hr, 3hr, 4hr, 5hr, 6hr, 8hr, 10hr, and 12hr (12hr taken at pre-dose). Days 4 – 6: Morning pre-dose PK samples collected for each dose Day 7: PK samples will be collected pre- dose and at

CONFIDENTIAL

208441
Protocol Amd 6

Procedure	Screening (Up to 28 days before Day 1)	Study Period (Days)									Follow-up (7-14 days post last dose) ¹ / Early Withdrawal ²	Notes
		-1	1	2	3	4	5	6	7	8		
											
the following time points post dose: 10min, 30min, 1hr, 1.5hr, 2hr, 2.5hr, 3hr, 4hr, 5hr, 6hr, 8hr, 10hr, 12hr and 14hr
 
PK samples will be collected at the following time points in case of TID administration: Day 1: pre-morning dose, 10min, 30min, 1hr, 1.5hr, 2hr, 2.5hr, 3hr, 4hr, 5hr, 6hr (6hr taken at pre-dose). Days 4 – 6: Morning pre-dose PK samples collected for each dose Day 6: PK samples will be collected pre-evening dose and at the following time points post evening-dose: 10min, 30min, 1hr, 1.5hr, 2hr, 2.5h,3hr, 4hr, 5hr and 6hr Day 7: PK samples will be collected pre-dose and at the following time points post dose: 10min, 30min, 1hr, 1.5hr, 2hr, 2.5hr, 3hr, 4hr, 5hr, 6hr, 8hr, 10hr, 12hr and 14hr Only one dose is administered on Day 7 The time points stated may be modified depending on emerging SAD and MAD PK profiles.
 
All samples collected will be 2mL in volume
	
Urine Sampling (metabolism)			←X→					←X→			
Pre-dose Day 1: An approx. 20ml urine sample will be taken. Post-dose Day 1: All urine from each participant will be collected from 0-24 hr post morning dosing. Day 6 All urine from each participant will be collected from 0-24 hr post morning dosing.
 
Urine volume and weight will be recorded. Details of urine collection and processing are described in the
	

CONFIDENTIAL

208441
Protocol Amd 6

Procedure	Screening (Up to 28 days before Day 1)	Study Period (Days)									Follow-up (7-14 days post last dose) ¹ / Early Withdrawal ²	Notes
		-1	1	2	3	4	5	6	7	8		
												SRM.
CCI												
Meals		X	X	X	X	X	X	X	X	X		
On Day 1 through to Day 7, participants will receive an adapted standard meal containing 35-40% fat 30 mins prior to each dosing.
 
Participants will receive standardized meals scheduled at the same time on each day.
 
Meals will be served as per the site schedule on Days -1 and Day 8.
 
Water is permitted on an ad lib basis apart from 1 hour prior to and after each dose administration. Doses will be taken with approximately 240 mL water.

AE review		←=====X=====→									X	
SAE review	X	←=====X=====→									X	
Concomitant medication review	X	←=====X=====→									X	

CONFIDENTIAL

208441
Protocol Amd 6

- 1) Follow-Up visit: If a participant meets the criteria of a participant with known COVID-19 positive contacts in the past 14 days, or is determined to have a high clinical index of suspicion for COVID-19, or has a positive laboratory confirmation (PCR or lateral flow test) of COVID-19 infection the Follow-Up visit may be deferred beyond 14 days after the last dose and scheduled/rescheduled at a timepoint as deemed appropriate by the Investigator.
- 2) Early Withdrawal visit: The Early Withdrawal Visit can be scheduled as needed and does not need to align with the duration allowed for the Follow-Up visit.

Any changes in the timing or addition of time points for any planned study assessments as the result of emerging pharmacokinetic data from this study must be documented and approved by the relevant study team member and then archived in the sponsor and site study files but will not constitute a protocol amendment. The Competent Authority (CA) and ethics committee (EC) will be informed of any safety issues that constitute a substantial amendment and require alteration of the safety monitoring scheme or amendment of the informed consent form (ICF). The changes will be approved by the CA and the EC before implementation.

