	AUC _{0-∞} (ng×h/mL)		C _{max} (ng/mL)		AUC _{0-∞} (ng×h/mL)		C _{max} (ng/mL)	
	mean	p95	mean	p95	mean	p95	mean	p95
20 ^s	552.8	906.5	86.8	133.2	88.1	53.7	70.3	45.8
60 ^s	1664.4	2757.2	262.3	381.5	29.3	17.7	23.3	16.0
150	4009.6	6737.1	646	957.5	12.1	7.2	9.4	6.4
300	8223.5	12960.2	1288.3	1874.8	5.9	3.8	4.7	3.3
450	12248.4	19950.1	1943.3	2991.7	4	2.4	3.1	2
650	17669.2	27663.7	2752.4	4091.4	2.8	1.8	2.2	1.5
900	24980.4	39885.6	3858.9	5501.1	1.9	1.2	1.6	1.1
1200 ^s	33082.9	53046.1	5186.9	7484.8	1.5	0.9	1.2	0.8

*The predicted human exposures are in blood and the animal exposures are in plasma. Human Blood to plasma ratio (B/P ratio = 0.88) is used for conversion of predicted blood exposures to obtain human plasma exposures.

[#]NOAEL exposures in female minipig: AUC = 48700 ng×h/mL; C_{max} = 6100 ng/mL. Safety margin = NOAEL exposure parameter value/predicted human plasma exposure parameter.

^sDose not included in simulations, exposure derived proportionally from simulated doses.

Figure 3 GSK3494245 predicted human systemic plasma exposures ($AUC_{0-\infty}$ & C_{max}) in scenario 1 and scenario 2 after single dose at various doses with anticipated variability

Scenario 1: CL=3.81 mL/min/kg and F=80%

Scenario 2: CL=6.67 mL/min/kg and F=64%

[figure not shown]

Table 6 Proposed dose levels for the MAD part of the study with exposure predictions and expected tox cover for the 95P of the population

BID Dose (mg)	Total Daily Dose (mg)	Cmax (ng.mL)		AUC0-24 (ng h/mL)		Tox cover for P95 to NOAEL	
		Mean	95 th percentile	Mean	95 th percentile	Cmax	AUC0-24h
30	60	464.1	891.4	1819	3282	6.8	14.8
60	120	862.4	1637	3828	6854	3.7	7.1

BID Dose (mg)	Total Daily Dose (mg)	Cmax (ng.mL)		AUC0-24 (ng h/mL)		Tox cover for P95 to NOAEL	
		Mean	95 th percentile	Mean	95 th percentile	Cmax	AUC0-24h
120	240	1603	3102	8057	14610	2.0	3.3
180	360	2303	4567	12450	22954	1.3	2.1
240	480	2978	6042	16955	31744	1.0	1.5

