7.1.5. ECG and Telemetry Stopping Criteria

A participant that meets either bulleted criterion based on the average of triplicate ECG readings will be withdrawn from study treatment.

QTc > 500 msec,

Change from baseline: QTc > 60 msec

- The *same* QT correction formula *must* be used for *each individual participant* to determine eligibility for and discontinuation from the study. This formula may not be changed or substituted once the participant has been enrolled. For example, if a participant is eligible for the protocol based on QTcB, then QTcB must be used for discontinuation of this individual participant as well.
- Once the QT correction formula has been chosen for a participant's eligibility, the *same formula* must continue to be used for that participant *for all QTc data being collected for data analysis*. Safety ECGs and other non-protocol specified ECGs are an exception.
- The average of triplicate ECG readings obtained over a brief (e.g., 5-10 minute) recording period.
- Withdrawal of participants is to be based on an average QTc value of triplicate ECGs. If an ECG demonstrates a prolonged QT interval, then obtain 2 more ECGs over a brief period of time and then use the mean QTc values of the 3 ECGs to determine whether the participant should be discontinued from the study.

OR

- Non-Sustained Ventricular Tachycardia (NSVT) > 3 beats or PVC triplets on telemetry.

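### As scheduled, the MAD part has no post-dose 12-lead ECG after Day 1, so a QTc effect that emerges with repeat dosing would be looked for only at trough

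*Protocol*

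**What the plan says.** The 12-lead ECG row of Protocol 1.3.2 gives a dense series on Day 1, at "subsequent time points post first-dose: 30 min, 1 hr, 1.5hr, 2hr, 2.5hr, 4hr, 6hr, 8hr 12hr and 14hr", and then "Day 2 to 7: 12-Lead ECG at pre-morning dose". Day 8 is blank, and the last ECG is at follow-up. Triplicates are confined to screening and the Day 1 pre-dose time. The same cell adds: "Timings will be reviewed as cohorts progress and may be adjusted to ensure appropriate measurements relative to peak concentrations for" subsequent cohorts.

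Other rows of the table continue after dosing late in the course:

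- Vital signs are taken 2, 4 and 6 h after the Day 7 morning dose, and at 24 h on Day 8.
- PK is sampled from 10 min to 14 h after the Day 7 dose. For TID there is also a profile to 6 h after the Day 6 evening dose.
- Telemetry is continuous for 48 h from the first dose and then "at least 24 hr post morning dose on Day 6".

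Protocol Section 3 and SAP 1.1.1 name 12-lead ECG among the primary endpoints for single and repeat doses. Protocol 7.1.5 applies its QTc withdrawal limits, including "Change from baseline: QTc > 60 msec", to the mean of triplicate 12-lead ECGs. Its telemetry criterion concerns non-sustained ventricular tachycardia and PVC triplets.

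**The concern.** The repeat-dose ECG endpoint is meant to show what seven days of dosing do to the ECG. After Day 1, every on-treatment ECG is placed 12 h after the preceding dose: under BID the doses are 12 h apart, and under TID they are at 0, 6 and 12 h, leaving a 12 h overnight gap. That is close to the lowest concentration of the day. The PK profiles on Days 6-7 therefore have no post-dose ECG beside them.

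Each MAD escalation decision (Protocol 4.6.3) follows seven days of dosing and includes review of individual ECGs. As scheduled, the committee sees no post-dose 12-lead interval data from after the first day. An effect that depends on repeat dosing and tracks concentration could look absent.

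**Working it through.** **Inputs.** Protocol 4.5.1 and Table 3: V = 1.28 L/kg; CL = 3.81 (low) or 6.67 (high) mL/min/kg; ka = 0.7 per h. Dose times: BID 0 and 12 h, TID 0, 6 and 12 h, with one morning dose on Day 7. Dose, F and V cancel in the ratios.

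**Reproducing the stated half-life.** k = CL × 0.06 / V.

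- Low clearance: 3.81 × 0.06 / 1.28 = 0.1786 per h, so t½ = 0.693 / 0.1786 = 3.88 h. This matches the approximately 4 h of Protocol 4.4.
- High clearance: 6.67 × 0.06 / 1.28 = 0.3127 per h, so t½ = 2.22 h.

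**Model.** One compartment with first-order absorption, summing over doses given at times d: C(t) ∝ Σ ka/(ka − k) × [exp(−k(t − d)) − exp(−ka(t − d))].

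**BID, low clearance, by hand.** ka/(ka − k) = 0.7 / 0.5214 = 1.3425.

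- Steady-state peak, 2.38 h after a dose: 1.3425 × (0.6537/0.8827 − 0.1890) = 0.7405.
- Pre-dose, 12 h after a dose: 1.3425 × (0.1173/0.8827 − 0.0002) = 0.178. Ratio: 0.178 / 0.7405 = 0.24.
- Day 1, 14 h (2 h after the second dose): 1.3425 × (0.0821 + 0.6996 − 0.2466) = 0.718. Ratio: 0.718 / 0.7405 = 0.97.

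**All cases, as a percentage of the steady-state daily peak:**

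| Time | BID low CL | BID high CL | TID low CL | TID high CL |
|---|---|---|---|---|
| Days 2-7, pre-morning (scheduled ECG) | 24 | 8 | 22 | 7 |
| Day 1, peak after first dose | 85 | 96 | 59 | 75 |
| Day 1, 14 h (scheduled ECG) | 97 | 100 | 98 | 99 |
| Day 7, peak after morning dose (no ECG) | 100 | 100 | 74 | 79 |
| Day 6, 2 h after evening dose (no ECG) | 99 | 100 | 100 | 99 |

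**Cross-check without a compartment model.** Protocol Table 6 gives BID predictions from preliminary SAD data. Average concentration is AUC(0-24)/24.

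- 30 mg: 1819/24 = 75.8, and 75.8/464.1 = 16% of mean Cmax.
- 240 mg: 16955/24 = 706.5, and 706.5/2978 = 24% of mean Cmax.

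The pre-dose level lies below the average, so it is below about 16-24% of peak. This agrees with the table.

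**Sensitivity.** If the half-life were 8 h (an assumption, not a document figure), the pre-dose ECG would be at 49-51% of peak and the Day 1 14 h ECG at 83-86%.

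**Pairing with PK.** Day 1 PK ends at 12 h for BID and 6 h for TID. The 14 h ECG therefore has no concurrent concentration under either regimen.

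**The case against.** The strongest reply is that Day 1 already does the job. The 14 h ECG is 2 h after the 12 h dose, and under linear PK it sits at 97-100% of the predicted steady-state peak. The Amendment 6 summary of changes shows similar care: the 8 h reading was added to match Tmax of the second TID dose. This stands for a direct effect of parent concentration. A reader might infer that QTc is never examined at steady-state peak concentrations, or that any QTc effect would be shrunk in proportion to the trough-to-peak ratio. Neither follows, because a linear parent-concentration effect would show at close to full size on Day 1. It does not stand for effects that need repeat dosing. Accumulation and time-invariance are secondary objectives, and Protocol 4.5.1 notes saturable hepatocyte clearance, so treating Day 1 as steady state assumes what the study sets out to learn.

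The 14 h reading is also single. Protocol 7.1.5 softens this by asking for two more ECGs when one shows a prolonged QT, but the pre-dose ECGs of Days 2-7 could trigger that only at trough.

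Second, the named cardiac risk is ventricular tachycardia in one mini-pig, and Day 6 telemetry spans the peaks of that day. That is correct, and it limits the gap to 12-lead intervals and QTc. The documents report no QT signal.

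Third, timings may be adjusted toward peak, and Protocol 1.3 lets this be done by Note to File. The clause shows the right intention, but it is discretionary and addresses later cohorts, so it secures nothing in a cohort run to the schedule as written.

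Finally, a reader might infer that ECG is the only primary safety measure without late post-dose readings. The schedule does not support that: MAD haematology and chemistry samples are taken fasted while every dose follows a meal, so those on Days 2-7 are most naturally pre-dose too.

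**Conclusion.** The point holds as a gap in the schedule as written: no post-dose 12-lead ECG after Day 1 of the MAD part, with Day 2-7 readings at roughly 7-24% of steady-state peak. The consequence is moderate. What goes unobserved is a time-dependent, metabolite-driven or delayed QTc effect, together with any paired post-dose ECG and PK data late in dosing. Exposure to near-peak parent concentration is not itself unobserved.

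The percentages rest on the Table 3 predictions, linear one-compartment PK and population-typical values. MAD dosing is fed, so actual Tmax may differ. Only the description of Days 2-7 as trough readings is independent of the model, since it follows from the dose times.

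**What to change.** In Protocol 1.3.2, reconcile the 12-lead ECG row with the late-course post-dose assessments already in the table:

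- **BID:** add ECGs after the Day 7 morning dose, for example at 2 and 4 h, where both vital signs and PK are scheduled.
- **TID:** add ECGs after the Day 6 evening dose at existing PK times around Tmax, for example 2 h and a neighbouring time. The Day 7 morning dose is the weaker choice here, because its peak is only 74-79% of the steady-state daily peak.

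These times match Day 1 readings by clock time (2 and 4 h for BID, 14 h for TID), which gives a within-participant comparison of first-day and late-course values.

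Keep the pre-dose ECGs of Days 3-5. Telemetry lapses from about the Day 3 morning dose until Day 6, so removing them would leave no scheduled cardiac recording in between.

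The cost is two or three more ECGs per participant while participants are in-house anyway. It can be offset by thinning the Day 1 series, provided the 14 h reading is kept. Writing the change into the schedule, rather than leaving it to a Note to File, makes it apply from the first MAD cohort.

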2. INTRODUCTION

2.1. Study Rationale

Visceral leishmaniasis (VL) is a parasitic disease caused by obligate intracellular protozoan parasites, particularly by the species *Leishmania donovani* and *Leishmania infantum/chagasi*. If left untreated, cases of VL are typically fatal. While therapies are available to treat the disease, none are ideal for use (due to toxicity, route of administration and cost) in resource poor settings where the disease is endemic. As such there is a real unmet medical need for new, short course oral drugs for the treatment of this disease.

The Phase 1 program will comprise a First Time in Human (FTIH) study of single ascending doses (SAD) and multiple ascending dose (MAD) in healthy participants, incorporating a food effect component to investigate the influence of food on the pharmacokinetics (PK) of GSK3494245. The study will evaluate the safety, tolerability and PK profile of SAD and MAD of GSK3494245. Results of this study are intended to be used to identify appropriate and well tolerated doses of GSK3494245 to be used in further studies. This study will be conducted at a single centre.

2.2. Background

Visceral leishmaniasis is identified as a Neglected Tropical Disease by the World Health Organisation. As a systematic approach to drug discovery is relatively new in this neglected disease, GSK3494245 was identified through a phenotypic screening approach. GSK3494245 is a highly selective *Leishmania* proteasome inhibitor for the treatment of visceral leishmaniasis (VL), acting on chymotrypsin like activity. This was established through comprehensive mode of action (MOA) studies utilising different approaches. GSK3494245 is believed to principally be an inhibitor of the ubiquitin-proteasome system (UPS) within the genus *Leishmania*, specifically the beta subunits of the 20s proteasome catalytic complex. The biochemical and molecular basis for the high selectivity of GSK3494245 to the *Leishmania* proteasome vs. human proteasome is described in [Wyllie, 2019](#).

More detailed information relating to non-clinical pharmacology, safety pharmacology, PK and metabolism, toxicology and other pre-clinical data can be found in the GSK3494245 Investigators Brochure (IB) [GlaxoSmithKline Document Number [RPS-CLIN-017065](#)].

2.3. Benefit/Risk Assessment

There is no direct benefit to the participants taking part in this study.

To date, GSK3494245 has not been administered to human participants; therefore, no clinical data are available. This is the first study proposed in human participants with GSK3494245.

The risk assessment of GSK3494245 is based on the pre-clinical studies conducted to date. Summaries of findings from these pre-clinical studies can be found in the Investigators Brochure (IB).

The proposed risk assessment and management plan for the study has been developed in accordance with the tenets of European Medicines Agency (EMA) guideline on strategies to identify and mitigate risks for FTIH clinical trials with investigational medicinal products [European Medicines Evaluation Agency (EMA)/ Committee for Medicinal Products for Human Use [EMEA/CHMP/SWP/28367/07](#)]. GSK has assessed this study for any risks that may be posed to participants taking part. Only healthy male participants will participate in this study.

In this study, safety will be monitored closely both by subjective reporting and by objective means, i.e. serial assessments of vital signs, clinical laboratory information and cardiac monitoring. The study will be run in a clinical unit with immediate access to hospital facilities for the treatment of medical emergencies. Participants will remain monitored in the clinic for the duration of each intervention period and will only be discharged from the unit at the end of each intervention period, if the investigator deems it safe to do so. In light of the coronavirus 2019 (COVID-19) pandemic, all participants will be screened for COVID-19 prior to, during and at the end of the study period.

More detailed information about the known and expected benefits and risks and reasonably expected adverse events of GSK3494245 may be found in the IB [GlaxoSmithKline Document Number [RPS-CLIN-017065](#)].

[figure not shown]
